 - For patients undergoing systemic treatment (alone or in combination with targeted treatment): If on post-treatment follow-up imaging within 3-12 months, lymph nodes seen on CT or MRI decrease by more than 30% in short axis diameter and PSA declines by more than 50%.

- If PSA increases by more than 50% on systemic therapy, then a increase in the size of lesion by more than 20% will be considered a true positive lesion.
- In subjects with localized suspected lymph node(s) receiving targeted treatment without concomitant systemic treatment there are two ways to meet true positive disease:
- If the subject shows a decrease of PSA by greater than 50% after targeted treatment and the lymph node does not enlarge (change in size less than 20% or less than 3 mm increase in short axis diameter) [OR]
 - If on post-treatment follow-up imaging within 3-12 months, lymph nodes seen on CT or MRI decrease by more than 30% in short axis diameter (with a minimum of 3 mm in change in size)
- For untreated patients: If on follow-up imaging within 3-12 months, lymph nodes seen on CT or MRI increase by more than 20% in short axis diameter (with a minimum of 3 mm in change in size).
- (2) False positive:
- For patients undergoing systemic treatment (alone or in combination with targeted treatment): If on post-treatment follow-up imaging within 3-12 months, lymph nodes seen on CT or MRI increase by more than 20% in short axis diameter and PSA decreases by more than 50%.
- In subjects with localized suspected lymph node(s) receiving targeted treatment without concomitant systemic treatment there are two ways to meet false positive disease:
- If the subject does not demonstrate a decrease of PSA by greater than 50% after targeted treatment [OR]
 - If on post-treatment follow-up imaging within 3-12 months, lymph nodes seen on CT or MRI increase by more than 20% in short axis diameter (with a minimum of 3 mm in change in size)
- For untreated patients: If on follow-up imaging within 3-12 months, lymph nodes seen on CT or MRI decrease by more than 30% in short axis diameter (with a minimum of 3 mm in change in size).
- (3) If all regions in a patient/region do not meet criteria for either True positive or False positive disease, then the patient/region will be considered inevaluable for primary endpoint.
- ii) Visceral lesions (non-lymph node soft tissue or organ) will be assessed by change in size. ⁶⁸Ga-PSMA-11 positive visceral lesions will be considered:
- (1) True positive:

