- For patients undergoing systemic treatment (alone or in combination with targeted treatment): If on post-treatment follow-up imaging within 3-12

months, lesions seen on CT or MRI decrease by more than 30% in long axis diameter and PSA declines by more than 50%.

- If PSA increases by more than 50% on systemic therapy, then a increase in the size of lesion by more than 20% will be considered a true positive lesion.

- In subjects with localized suspected lesions(s) receiving targeted treatment without concomitant systemic treatment there are two ways to meet true positive disease:

- If the subject demonstrates a decrease of PSA by greater than 50% after targeted treatment [OR]
- If on post-treatment follow-up imaging within 3-12 months, lesions seen on CT or MRI decrease by more than 30% in long axis diameter (with a minimum of 3 mm in change in size)

- For untreated patients: If on follow-up imaging within 3-12 months, lesions seen on CT or MRI increase by more than 20% in long axis diameter (with a minimum of 3 mm in change in size).

(2) False positive:

- For patients undergoing systemic treatment (alone or in combination with targeted treatment): If on post-treatment follow-up imaging within 3-12 months, lesions seen on CT or MRI increase by more than 20% in long axis diameter and PSA decreases by more than 50%.

- In subjects with localized suspected lesions(s) receiving targeted treatment without concomitant systemic treatment there are two ways to meet false positive disease:

- If the subject does not demonstrate a decrease of PSA by greater than 50% after targeted treatment [OR]
- If on post-treatment follow-up imaging within 3-12 months, lesions seen on CT or MRI increase by more than 20% in long axis diameter (with a minimum of 3 mm in change in size)

- For untreated patients: If on follow-up imaging within 3-12 months, lesions seen on CT or MRI decrease by more than 30% in long axis diameter (with a minimum of 3 mm in change in size).

(3) If all regions in a patient/region do not meet criteria for either True positive or False positive disease, then the patient/region will be considered inevaluable for primary endpoint.

iii) ⁶⁸Ga-PSMA-11 positive bone lesions will be considered:

(1) True positive:

- If there was a corresponding positive sclerotic lesion on the CT portion of the ^{68}Ga -PSMA-11 PET or on a separate CT obtained ≤ 30 days before or after the PET/CT in the same location as the PSMA uptake.

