- If there is focal uptake seen in the same location as the PSMA uptake on the baseline bone scan performed within one month of ^{68}Ga -PSMA-11 PET.
- If there is a lesion noted in the same location as the PSMA uptake on the initial MRI performed within one month of ^{68}Ga -PSMA-11 PET.
- If within 12 months follow-up CT demonstrates development of sclerosis in the same location as the PSMA uptake.
- If within 12 months follow-up MRI demonstrates a new bone lesion in the same location as the PSMA uptake.
- If within 12 months follow-up bone scan demonstrates new focal uptake in the same location as the PSMA uptake.
- In subjects with localized suspected bone lesion(s) receiving targeted treatment without concomitant systemic treatment:
 - o If the subject demonstrates a decrease of PSA by greater than 50% after targeted treatment.

(2) False positive:

- In subjects with localized suspected bone lesion(s) receiving targeted treatment without concomitant systemic treatment:
 - o If the subject does not demonstrate a decrease of PSA by greater than 50% after targeted treatment with curative intent (ie non-palliative radiation).
- If ^{68}Ga -PSMA-11 positive bone lesions do not meet the criteria for true positive findings, and appropriate correlative and follow-up imaging was acquired.

(3) If bone lesions do not meet criteria for either true positive or false positive disease listed above, then the patient/region will be considered inevaluable for primary endpoint.

iv) ^{68}Ga -PSMA-11 positive prostate bed and prostate lesions will be considered:

(1) True positive:

- For patients undergoing systemic treatment (alone or in combination with targeted treatment): If on post-treatment follow-up imaging within 3-12 months, lesions seen on CT or MRI decrease by more than 30% in long axis diameter
- In subjects with localized suspected lesions(s) receiving targeted treatment without concomitant systemic treatment there are two ways to meet true positive disease:

- If the subject demonstrates a decrease of PSA by greater than 50% after targeted treatment [OR]
- If on post-treatment follow-up imaging within 3-12 months, lesions seen on CT or MRI decrease by more than 30% in long axis diameter (with a minimum of 3 mm in change in size)

- For untreated patients: If on follow-up imaging within 3-12 months, lesions seen on CT or MRI increase by more than 20% in long axis diameter (with a minimum of 3 mm in change in size).

(2) False positive:

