- (2) True negative patient: in the absence of True Positive or False Positive lesions, a patient will be considered a True Negative if there is pathology that is negative for disease and corresponding lesion is negative by PSMA PET.
 - (3) False positive patient:
 - (a) Pathology confirms a false positive lesion that is read as positive on PSMA PET.
 - (b) In the absence of pathology: there are no true positive regions, and there is a region that is categorized as false positive based on imaging or clinical follow-up.
 - (4) False negative patient: in the absence of True Positive or False Positive lesions, a patient will be considered a False Negative if there is pathology that is positive for disease and corresponding lesion is negative by PSMA PET. Additionally, patients without evidence of disease on PSMA PET but with biochemical evidence of disease will be considered a False Negative.
- ii) Region level evaluation: Each patient will have four evaluable regions (Table 1: prostate bed, pelvis, extrapelvic soft tissue, and bone metastases). Each region will be categorized as true positive or false positive as described above. Regions without evidence of PSMA positive disease or deemed inevaluable will not be included in the analysis.
 - (1) True positive region:
 - (a) Pathology confirms a PSMA avid lesion as a true positive in the region.
 - (b) In the absence of pathology, clinical or imaging follow-up demonstrates a true positive lesion within the region independent of the presence of an inevaluable lesion or a false positive lesion
 - ie true positive disease will supersede a false positive lesion in the region based analysis if based on imaging/clinical follow-up
 - (2) True negative region: in the absence of True Positive or False Positive lesions within a region, the region will be considered a True Negative if there is pathology that is negative for disease in the region and corresponding lesion is negative by PSMA PET.
 - (3) False positive region:
 - (a) Pathology confirms a PSMA avid lesion as a false positive in the region

- (b) In the absence of pathology, there are no true positive lesions in the region, and there is a false positive lesion by clinical or imaging follow-up.
- (4) False negative region: in the absence of True Positive or False Positive lesions in a region, the region will be considered a False Negative if there is pathology that is positive for disease in the region and corresponding lesion is negative by PSMA PET.

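### After targeted treatment alone, the true-positive and false-positive criteria in 8.3.2 b) overlap, and no rule says how to label a lesion that meets both

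*Combined protocol and SAP*

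**What the plan says.** Section 8.3.2, Reference Standard Definition b), sets follow-up criteria by lesion type and by treatment received. For a lymph node in a patient given targeted treatment alone, there are two TP routes and two FP routes, each pair joined by OR:

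- TP by PSA: "If the subject shows a decrease of PSA by greater than 50% after targeted treatment and the lymph node does not enlarge".
- TP by size: "lymph nodes seen on CT or MRI decrease by more than 30% in short axis diameter (with a minimum of 3 mm" as the smallest change that counts). There is no PSA condition.
- FP by PSA: "If the subject does not demonstrate a decrease of PSA by greater than 50% after targeted treatment [OR". There is no size condition.
- FP by size: "lymph nodes seen on CT or MRI increase by more than 20% in short axis diameter (with a minimum of 3 mm" as the smallest change). There is no PSA condition.

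Visceral and prostate-bed lesions follow the same layout in long-axis diameter, but their PSA route to TP is only "If the subject demonstrates a decrease of PSA by greater than 50% after targeted treatment [OR", without the non-enlargement condition.

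Bone is built differently. An imaging correlate at baseline, or a new one within 12 months, is enough for TP whatever the PSA does. One FP route is "If the subject does not demonstrate a decrease of PSA by greater than 50% after targeted treatment with curative intent". The other applies only when no TP criterion is met.

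For every lesion type, the inevaluable clause covers findings that meet neither list.

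Section 8.3.2 d) then combines lesions. At region level, in the absence of pathology, the rule is "ie true positive disease will supersede a false positive lesion in the region based analysis if based on imaging/clinical follow-up". At patient level, one TP lesion makes the patient TP even if other regions are FP on follow-up. Pathology ranks above follow-up, a pathology FP region outweighs follow-up TP regions, and investigators may depart from the criteria if this is recorded.

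**The concern.** A reference standard should give one label for one set of evidence. Here, PSA and imaging can point in opposite directions and each is sufficient alone, so the same lesion can be TP on one line and FP on another. This is a contradiction between stated rules rather than missing detail.

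The labels feed per-patient and per-region sensitivity (primary) and PPV (first secondary endpoint). Section 8.3.2 defines success as 70% per-patient sensitivity for two of three readers, and 8.2.1 also plans around 70%, so the TP count matters near that line. Under 8.1.2, follow-up images are read locally by readers who know all results and are told where the PET-positive lesions are. Leaving conflicting lesions to case-by-case judgement would therefore mean unblinded labelling.

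**Working it through.** **1. Enumerate the rules (targeted treatment alone).** Cross PSA fall above 50% (yes/no) with size (shrinks >30%, stable, grows >20%; at least 3 mm for either change).

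| PSA fall >50% | Size | Node | Visceral, prostate bed |
|---|---|---|---|
| Yes | Shrinks | TP | TP |
| Yes | Stable | TP | TP |
| Yes | Grows | FP | **TP and FP** |
| No | Shrinks | **TP and FP** | **TP and FP** |
| No | Stable | FP | FP |
| No | Grows | FP | FP |

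For bone, cross PSA fall with imaging (correlate; none although imaging was acquired; imaging not acquired). With curative-intent treatment, the cell with no PSA fall and a correlate is both TP and FP. With palliative treatment, no cell is both. Cells meeting both lists are therefore 1 of 6 for nodes, 2 of 6 for visceral, 2 of 6 for prostate bed, and 1 of 6 (curative) or 0 of 6 (palliative) for bone.

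**2. Compare the growth cell across the protocol.** Growth above 20% with a PSA fall above 50% is FP only for nodes after targeted treatment. It is also FP for visceral and prostate-bed lesions under systemic treatment. Only visceral and prostate-bed lesions after targeted treatment can be TP on that evidence, because the node condition was not carried over.

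**3. Follow a dual lesion through 8.3.2 d).** Without pathology, a region is FP only if it contains no TP lesion, and a patient is FP only if there is no TP region. A lesion on both lists satisfies the TP condition and blocks the FP condition, so the literal result is TP.

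**4. Size.** The plan states no figure for the overlap, so there is none to reproduce. Its planning figure of 75 is not disputed: [(2.326×√0.25 + 1.282×√0.21)/0.2]² = 76.6, so 77, within 2 of 75.

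Inputs for an illustration:

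- PET-negative 24% (8.2.1), so PET-positive 76%. PET-negative patients with biochemical disease count as false negative (FN), per 8.3.2 d).
- PPV 87% when dual lesions count as TP. This is an assumption. It borrows the first-cohort biopsy figure in 8.2.1, which is labelled specificity although that cohort had no true negatives.
- All PET-positive patients are evaluable (assumption).
- d = share of PET-positive patients whose TP status rests only on a dual lesion. It is not in the documents; the range taken is 5 to 20%.

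Formulas:

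- Sensitivity, dual as TP: 0.76×0.87/(0.76×0.87 + 0.24) = 0.6612/0.9012 = 73.4%.
- Sensitivity, dual as FP or inevaluable: 0.76(0.87−d)/[0.76(0.87−d) + 0.24].
- PPV, dual as FP: 0.87−d. PPV, dual excluded: (0.87−d)/(1−d).

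| d | Sensitivity, dual not TP | PPV, dual as FP | PPV, dual excluded |
|---|---|---|---|
| 0 | 73.4% | 87.0% | 87.0% |
| 5% | 72.2% | 82.0% | 86.3% |
| 10% | 70.9% | 77.0% | 85.6% |
| 20% | 68.0% | 67.0% | 83.8% |

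Sensitivity equals 70% when 0.76(0.87−d) = 0.24×0.7/0.3 = 0.56, so d = 0.87 − 0.7368 = 13.3%.

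**5. Per region.** Sensitivity is TP/(TP+FN). With FN = 0 it is 100% under any label. With 75 TP and 5 FN, removing 10% of the TPs moves it from 75/80 = 93.8% to 67.5/72.5 = 93.1%.

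**The case against.** The strongest reply is that the endpoints are per patient and per region, and 8.3.2 d) gives an order at those levels: TP beats FP when both come from follow-up. On that reading the outcome is determinate and only a clarifying sentence is missing. The order does exist. But the region sentence is worded for a TP finding set against an FP lesion in the same region, and the patient rule for conflict with other regions. Neither addresses one lesion that contradicts itself. If they are stretched to cover it, the result is always TP, which should be a stated choice and not a by-product.

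Several stronger readings are tempting, and the documents do not support them:

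- *That TP-first is the only tie-break.* Pathology outranks follow-up, a pathology FP region outweighs follow-up TP regions, and recorded departures are allowed.
- *That every discordant lesion becomes TP.* A node that grows while PSA falls is FP only, which works against the test.
- *That bone shares the same structure.* It has no PSA-or-size pair, and its PSA route to FP requires curative intent and localized suspected disease.
- *That a handful of lesions would decide the trial.* One can construct 53/75 = 70.7% turning into 48/70 = 68.6%. But 53 is the smallest passing count, the 5 are invented, and 75 belongs to the per-region calculation. The 70% success rule is per patient, for which 8.2.1 gives 107.

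It is also fair to say that a patient leaves the TP count only if a dual lesion is the sole TP evidence, and only in the targeted-only subgroup, whose size is not stated. Finally, adding the node condition makes growth with PSA fall FP while the mirror case stays open. That asymmetry follows the protocol's own labels for growth with PSA fall.

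**Conclusion.** The criteria are wrong as written. At all four lesion types one lesion can meet both lists, no lesion-level rule resolves it, and the literal precedence favours the test.

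A reader might infer that sensitivity and PPV are therefore inflated. The documents do not show that. For shrinkage without a PSA fall, nothing in them establishes that TP is the wrong label. For growth with a PSA fall, they do show that TP is inconsistent with the protocol's own rules elsewhere.

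Under the stated assumptions, the choice of label is worth about 1.2 to 5.4 points of per-patient sensitivity for a dual share of 5 to 20%, and the 70% line is crossed only above about 13%. PPV is more exposed: 5 to 20 points if dual lesions are FP, but only 0.7 to 3.3 if they are excluded. Per-region sensitivity does not move when FN = 0. These figures depend on an unknown dual share, on 87% as PPV and on full evaluability of PET-positive patients.

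**What to change.** Before any lesion is classified, amend 8.3.2 b) so that the categories are mutually exclusive:

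1. Add to the visceral and prostate-bed PSA route to TP the non-enlargement condition already used for nodes, expressed in long-axis diameter (change under 20% or increase under 3 mm).
2. State one lesion-level rule for the remaining dual lesions: shrinkage without a PSA fall above 50%, and bone with a correlate but no such fall after curative-intent treatment. Inevaluable in the primary analysis is one workable choice.
3. Report the number of dual lesions. Give per-patient sensitivity with them counted as TP and as inevaluable, and PPV with them counted as TP, as FP and as inevaluable. An FP version of sensitivity adds nothing, because FP does not enter TP/(TP+FN).

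The cost is a few sentences and one extra table. If the inevaluable rule is chosen, a few lesions drop out of the primary analysis.

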3.3.1 Inclusion Criteria

1. Histopathologically proven prostate adenocarcinoma.
2. Rising PSA (at least two consecutive rising PSAs) after definitive therapy with prostatectomy or radiation therapy (external beam or brachytherapy).
 - a. Post radical prostatectomy (RP) – AUA recommendation for biochemical recurrence after radical prostatectomy
 - i. PSA greater than or equal to 0.2 ng/mL measured more than 6 weeks after RP.

- b. Post-radiation therapy –ASTRO-Phoenix consensus definition of biochemical recurrence after radiation therapy
 - i. Nadir + greater than or equal to 2 ng/mL rise in PSA
3. Karnofsky performance status of ≥ 50 (or ECOG/WHO equivalent).
4. Age > 18.
5. Ability to understand a written informed consent document, and the willingness to sign it.

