8.3.2 Analysis of Primary Endpoints

Sensitivity on a per-patient and per-region-basis of ^{68}Ga -PSMA-11 PET for detection of tumor location confirmed by histopathology/biopsy, clinical and conventional imaging follow-up will be calculated and reported along with the corresponding two-sided 95% confidence intervals. The confidence intervals will be constructed using the Wilson score method. For successful completion of the primary endpoint, two of the three readers will need to have an 70% sensitivity for the detection of disease on a per patient level for the cases that have a) imaging follow-up, b) pathology correlation or c) combination of pathology and imaging follow-up and/or pathology correlation.

^{68}Ga -PSMA-11 PET Results Definition

a) Imaging interpretation ^{68}Ga -PSMA-11 PET:

Local Interpretations: PET images will initially be interpreted by a board certified nuclear medicine physician or a board-certified radiologist experienced in reading PET at the time of the imaging study at the institution that the study is being performed. These interpretations will not be used for final evaluation, and will not be reported as part of the primary or secondary endpoints.

Central Read Logistics: Imaging data will be anonymized and collected at a central site. PET data will be interpreted by three different readers in a random order at separate reading sessions. Cross sectional imaging (CT or MRI) from the ^{68}Ga -PSMA-11 PET will be available for anatomic correlate. The Central readers will be blinded to all other imaging results and all other clinical data.

Reader Positivity and Negativity Definition: Regions defined in Table 1 will be graded for the presence of suspected disease on a two-point scale by each reader (0=Negative or 1=Positive). A region will be judged as positive if at least one lesion in this region is visually positive.

Reader Training: ^{68}Ga -PSMA-11 PET/CT reading training set and guides will be provided and completion of this training will be required for all central review readers. Common pitfalls will be reviewed as part of the reader training.

Criteria for visual interpretation:

Regions of suspected disease will be graded on a two-point scale by each blinded reader (0=Negative or 1= Positive). A region will be judged as positive if at least one lesion in this region is visually positive.

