- For patients undergoing systemic treatment (alone or in combination with targeted treatment): If on post-treatment follow-up imaging within 3-12 months, lesions seen on CT or MRI increase by more than 20% in long axis diameter and PSA decreases by more than 50%.

- In subjects with localized suspected lesions(s) receiving targeted treatment without concomitant systemic treatment there are two ways to meet false positive disease:

- If the subject does not demonstrate a decrease of PSA by greater than 50% after targeted treatment [OR]
- If on post-treatment follow-up imaging within 3-12 months, lesions seen on CT or MRI increase by more than 20% in long axis diameter (with a minimum of 3 mm in change in size)

- For untreated patients: If on follow-up imaging within 3-12 months, lesions seen on CT or MRI decrease by more than 30% in long axis diameter (with a minimum of 3 mm in change in size).

(3) If the lesion does not meet criteria for either True positive or False positive disease, then the lesion will be considered inevaluable for primary endpoint.

c) Histopathology/Biopsy:

- i) ⁶⁸Ga-PSMA-11 positive findings are aimed to be confirmed by histopathology/biopsy if clinically feasible. Pathology performed 60 days before the PSMA PET will be available for correlation.
- ii) Histopathological procedures and biopsies will be performed as clinically indicated and as per institutional protocol.

(1) Positive Histopathology/Biopsy: Confirmed sites of metastatic or tumor involvement by histopathology/biopsy will be discussed with the responsible physician/surgeon.

- (a) True Positive: lesion is positive on targeted biopsy/surgical sampling and is read as positive on PSMA PET.
- (b) False Negative: lesion is positive on targeted biopsy/surgical sampling and is read as negative on PSMA PET.

- (2) **Negative Biopsy:** Patients with suspected tumor recurrence on ^{68}Ga -PSMA-11 PET with negative histopathology/biopsy will be handled as outlined below:
- (a) Lymph nodes:
- For patients undergoing nodal dissection: Patients will be rescanned with dedicated CT, MRI or a repeat ^{68}Ga -PSMA-11 PET to determine if the suspicious ^{68}Ga -PSMA-11 positive node was removed.
 1. If ^{68}Ga -PSMA-11 positive lymph node is still present, a repeat biopsy can be pursued if clinically feasible and applicable, or follow-up using imaging as described above will be performed.
 2. If the corresponding node was removed, then this will be considered a False Positive.

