 - For patients undergoing needle biopsy: Images of the procedure will be reviewed to determine if the correct node was biopsied.
 1. If the correct node was biopsied, then a negative biopsy will be considered a False Positive.
 2. If the incorrect node was biopsied, then follow-up imaging as described above will be performed.
- (b) Bone lesions: Given the high rate of false negative biopsies for osseous metastases in patients with prostate cancer, patients with negative bone biopsies of PSMA PET positive lesions will be further evaluated:
- If pathology demonstrates an alternative diagnoses that is known to be PSMA positive (eg Renal Cell Carcinoma metastases, Paget's disease), then this will be considered a False Positive.
 - If pathology is indeterminate, then follow-up imaging as described above will be performed.
- (3) Although not routinely performed during standard practice, immunohistochemical staining for PSMA of tumor specimens (primary and lymph node metastases) may be performed, although not required.
- d) Definitions of True Positive, False Positive, True Negative, and False Negative patients and regions: Pathology will be considered superior to imaging and clinical follow-up when available as described below. Patient and region level classification will be performed for each blinded reader, and be reported separately. The following criteria serve as a guide for interpretation. However not all findings on a lesions, region and patient level can be detailed here and investigators may deviate from these criteria in individual patients. These will be recorded for each interpretation that is not described in this protocol for the definition of a region or patient.
- i) Patient level evaluation:
- (1) True positive patient: A single region in a patient contains a true positive node either by pathology or imaging/clinical follow-up.

- (a) For a patient to be considered a True Positive, only one region is required to have a true positive lesion as described above, unless one region is categorized as a false positive based on pathology. This means that a single pathology false positive region outweighs regions with imaging/clinical follow-up true positive disease.
 - (b) A patient will be considered a True Positive if one region contains a lesion that is True Positive, even if other regions are categorized as inevaluable or false positive based on imaging or clinical follow-up.

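### Unverifiable PET-positive men leave the primary per-patient sensitivity while PET-negative men can count as false negatives on PSA alone, so exclusion depends on the PET result and can differ between readers

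*Combined protocol and SAP*

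**What the plan says.** Section 8.3.2 b) sets reference-standard rules for PET-positive findings only. For lymph nodes, visceral lesions and bone, if neither set of criteria is met, "then the patient/region will be considered inevaluable for primary endpoint". For prostate bed the rule is written at lesion level: "then the lesion will be considered inevaluable for primary endpoint". Bone has a further default. PET-positive bone lesions are false positive if they "do not meet the criteria for true positive findings, and appropriate correlative and follow-up imaging was acquired".

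For PET-negative men, 8.3.2 d) i) (4) says that "patients without evidence of disease on PSMA PET but with biochemical evidence of disease will be considered a False Negative". Inclusion criterion 2 in 3.3.1 asks every enrolled man for "Rising PSA (at least two consecutive rising PSAs) after definitive therapy", so biochemical evidence is present at entry in all of them. Section 8.3.2 d) i) (2) also provides that, absent true- or false-positive lesions, "a patient will be considered a True Negative if there is pathology that is negative for disease" and the corresponding lesion is PET-negative.

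On readers, 8.3.2 d) states: "Patient and region level classification will be performed for each blinded reader, and be reported separately". The opening paragraph of 8.3.2 sets the success rule: "two of the three readers will need to have an 70% sensitivity for the detection of disease on a per patient level". It limits that rule to cases with imaging follow-up, pathology or a combination. Section 8.3.1 instead limits the Primary Aim to patients with histopathology.

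**The concern.** Sensitivity is TP/(TP+FN). A PET-positive man enters that fraction only if a lesion is verified as true positive. If he is inevaluable, he leaves numerator and denominator together. A PET-negative man can enter as a False Negative on PSA alone, yet the same PSA evidence does not keep an unverified PET-positive man in the analysis. The exclusion can therefore remove true positives but not PSA-defined false negatives.

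Follow-up imaging does not remove the problem. An untreated node that is stable on the follow-up scan meets neither rule in 8.3.2 b) i). Take a 5 mm node as an example: the 3 mm minimum is a 60% change (3/5). A stable node under systemic treatment also meets neither rule. A PET-negative man with the same follow-up scan can be counted as a False Negative.

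The exclusion is also reader-specific. A man with one unverifiable node is dropped for a reader who calls it. If a second reader calls nothing, he is a False Negative for that reader. At stake is whether the two-of-three 70% rule compares like with like, and whether passing or failing it reflects detection or the pattern of verification.

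**Working it through.** **The plan's own figures.** Section 8.2.1 asks for 75 cases (50% null, 70% alternative, one-sided 0.01, 90% power). The normal approximation gives (2.326×0.5 + 1.282×0.458)²/0.2² = 76.6, close to 75. Then 75/0.20 = 375 men with biopsy or imaging follow-up, and 75/0.70 = 107 for the per-patient analysis. None of these steps includes an allowance for inevaluable men, and no expected inevaluable share is given.

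**Inputs**
- PET-negative share: 24% (8.2.1), so PET-positive 76%. The four listed regions sum to 77%; using 77% moves the 15.3% crossing below only to 16.4%.
- Confirmed share of verified PET-positives (PPV): 87%. This is an assumption. Section 8.2.1 prints 87% as specificity, but it also reports no true negatives, so I read it as PPV. Range shown: 80% to 100%.
- u, the inevaluable share of PET-positive men: not in the documents, so varied.
- f, the share of PET-negative men counted: 1 under 8.3.2 d) i) (4) read alone; lower if 8.3.1, the success rule's case restriction or the True Negative rule removes some.

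**Formula**

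Sensitivity = 0.76·PPV·(1−u) / [0.76·PPV·(1−u) + 0.24·f]

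**All PET-negative men counted (f = 1), PPV 87%**

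0.76×0.87 = 0.6612.
- u = 0: 0.6612/0.9012 = 73.4%
- u = 10%: 0.5951/0.8351 = 71.3%
- u = 20%: 0.5290/0.7690 = 68.8% (4.6 points lower than at u = 0)
- u = 50%: 0.3306/0.5706 = 57.9%

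The 70% crossing needs TP = (0.7/0.3)×0.24 = 0.56, so u = 1 − 0.56/0.6612 = 15.3%. With PPV 80% it is 1 − 0.56/0.608 = 7.9%; with PPV 100%, 1 − 0.56/0.76 = 26.3%.

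**Half the PET-negative men counted (f = 0.5), PPV 87%**
- u = 0: 0.6612/(0.6612 + 0.12) = 84.6%
- 70% crossing: u = 1 − 0.28/0.6612 = 57.7%

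If no PET-negative men are counted, patient-level sensitivity in this model is 100% by construction.

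**Reader denominators (hypothetical counts).** A reader has 70 true positives and 30 False Negatives: 70/100 = 70%. If he also calls unverifiable sites in 10 of those 30, they leave as inevaluable: 70/90 = 77.8%, with no further verified detection.

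**Bounds at u = 20% (f = 1, PPV 87%).** Inevaluable men are 0.76×0.20 = 0.152 of the set.
- Complete case: 68.8%
- All counted as true positive: (0.5290 + 0.152)/(0.5290 + 0.152 + 0.24) = 73.9%
- All counted as not detected: 0.5290/(0.5290 + 0.152 + 0.24) = 57.4%

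The lower bound is demanding. It falls below 70% once 0.3×0.6612(1−u) < 0.7×(0.24 + 0.76u), that is, above u = 4.2%. In the reader example the bounds are 70/100 = 70% and 80/100 = 80%, so over-calling no longer raises the lower one.

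**The case against.** **PET-negative men can also leave.** A reader might infer that they are never inevaluable. The documents do not support that. Section 8.3.1 restricts the Primary Aim to histopathology, the success rule needs follow-up or pathology, and a PET-negative man with negative pathology can be a True Negative. Section 8.2.1 describes biopsies after a positive PET, so PET-negative men may well be verified less often. That would push sensitivity up. This objection stands, and it is why neither a fixed 15% threshold nor a downward bias can be asserted.

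**Inevaluability is narrower than it looks.** After targeted treatment without systemic therapy, the PSA response settles most cases one way or the other. Bone can be confirmed on baseline imaging and defaults to false positive when appropriately imaged. One true-positive region makes the patient true positive even if other regions are inevaluable. All of this limits u but does not make it zero, and false positives leave TP+FN too.

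**Confirmation is part of the endpoint.** The objective is detection of tumor location as confirmed by pathology or follow-up. It would therefore be too strong to say that the endpoint merely measures how verifiable lesions are. PET-positive share and PPV also drive it. The unequal treatment of the two PET results remains.

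**Readers cannot exploit the rule deliberately.** Central readers are blinded to clinical data and other imaging and cannot know which sites will prove unverifiable. The example above has no source in the plan; it shows only that denominators can differ.

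**A further inference to avoid.** With 375 of 1,500 men verified, one might set 375 against 1,140 PET-positive men, call 67% inevaluable, and obtain 375×0.87/(375×0.87 + 360) = 47.5%. That counts all 360 PET-negative men while dropping PET-positive men who were not followed up. The success rule is limited to cases with follow-up or pathology, so the documents do not support the figure.

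**Conclusion.** The concern holds in a conditional form. The text makes exclusion from the primary per-patient sensitivity depend on the PET result, and it allows three readers to be judged by one 70% rule on different denominators. If all PET-negative men count, PPV is 87% and the followed-up set has the 76/24 PET mix, the margin over the bar is 3.4 points with no inevaluable men and is gone at about 15% inevaluable (8% to 26% over the PPV range). If half the PET-negative men count, the crossing moves to about 58%. Which case applies cannot be settled, because 8.3.1, the opening of 8.3.2 and 8.3.2 d) i) are not reconciled and no inevaluable share is projected. What is established is that verification patterns alone can move the primary result across the bar, in either direction.

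**What to change.** 1. Reconcile 8.3.1, the case restriction in the opening paragraph of 8.3.2, and the False Negative and True Negative rules in 8.3.2 d) i) into one per-patient analysis set. Define it without reference to the PET result and use it for all three readers. State which classification applies when a PET-negative man has both negative pathology and biochemical evidence of disease.
2. Keep inevaluable PET-positive men in that set. For each reader, report their number and three sensitivities: the current complete-case figure, the figure with all of them counted as true positive, and the figure with all counted as not detected.
3. State whether the 70% conclusion holds at both bounds for at least two readers.
4. A verification-weighted estimate may be added as a sensitivity analysis only. It assumes that verified and inevaluable positives are alike, which is doubtful when being inevaluable often means that the lesion did not change enough. It also rewards over-calling. In the reader example with 87% confirmed, 70 true positives imply 70/0.87 = 80.5 verified positives. Weighting up for the 10 extra calls gives 70×90.5/80.5 = 78.7, and 78.7/98.7 = 79.7%, above the 77.8% from complete cases.

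The common set does not equalise everything: verified false positives still leave TP+FN reader by reader. The cost is SAP wording and a little more analysis on data already collected, with a possibly less favourable or less definite primary conclusion.
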